### 2.3.2 KNOWN POTENTIAL BENEFITS

There are no anticipated short- or long-term benefits to an 8-week administration of transdermal 17 $\beta$  estradiol in postmenopausal women.

### 2.3.3 ASSESSMENT OF POTENTIAL RISKS AND BENEFITS

It is becoming clear that risks for cognitive decline may be different between the sexes. Even if overall risk is the same, it may be that, as in heart disease, different factors contribute risk to development of dementia. Evidence from animal work suggests that the effects of estrogen on bioenergetic pathways may be an important risk factor contributing to long-term declines in glucose uptake in the brain in women, a known precursor to Alzheimer's disease, and a shift in bioenergetic fuel source to more reliance on ketone bodies. This has implications both for administration of estrogen in healthy states, and in common metabolic diseases, such as T2D. However, proof of this theory in humans is entirely absent. A potential mechanism for interaction between common diseases and estrogen is important, because it might lead to changes in the prescribing of estrogens.

The Women's Health Initiative Memory Study (WHIMS) initially published that oral administration of conjugated equine estrogens increased risk for cognitive decline. However, our recent reanalysis of the data taking diabetes status into account showed that the presence of T2D largely accounted for this effect.

While there is no anticipated direct benefit of this study, risks are temporary and reversible. There is a body of literature that examined estrogen therapy as a means to prevent Alzheimer's disease. Multiple studies were published in this age range with this or higher dosage, both transdermal and oral routes, but longer duration of estrogen administration. Across these studies, side effects were minimal until after 12 weeks of administration, which is 4 weeks longer than the proposed administration here. The study team has planned frequent monitoring to minimize risks further.

## 3 OBJECTIVES AND ENDPOINTS

OBJECTIVES	ENDPOINTS	JUSTIFICATION FOR ENDPOINTS
Primary:		

OBJECTIVES	ENDPOINTS	JUSTIFICATION FOR ENDPOINTS
To assess whether 8-week administration of estrogen alters brain glucose and ketone body uptake in women with and without type 2 diabetes.	Brain uptake of glucose and ketone bodies using [F-18]FDG PET and [C-11]AcAc PET.	Using PET tracers allows direct measurement of ketone and glucose uptake to the brain.
Secondary		
To assess whether 8-week administration of estrogen alters cognitive test scores in women with and without type 2 diabetes.	Composite scores of memory and executive function.	The cognitive tests selected are commonly used to assess for dementia and dementia risk.

## 4 STUDY DESIGN

### 4.1 OVERALL DESIGN

This is an investigation of the effects of transdermal estrogen administration on brain uptake of glucose and ketone bodies in postmenopausal women with and without T2D. The main hypothesis is that estrogen affects brain metabolism of ketone bodies and glucose differently in women with T2D and those without, in accordance with the healthy cell bias theory of estrogen action. All women will be tested before and after 8-week estrogen administration. It is a single-site study with two comparison groups: one with T2D (n=10) and one without (n=10). Randomization is not possible, as the comparison is between women affected and unaffected by T2D (and women cannot be randomized to have T2D). The study will include women of European American and African American descent and with Hispanic ethnicity in proportion to the local population for this age group. No interim analysis is planned.

### 4.2 SCIENTIFIC RATIONALE FOR STUDY DESIGN

This study will compare the effects of estrogen on brain uptake of glucose and ketone bodies in women with and without T2D. We are comparing women with and without T2D because T2D is a potent risk factor for dementia that may differentially affect women. Type 2 diabetes (T2D) affects an estimated 26% of people over the age of 65 and increases the risk for dementia by 50-60%. T2D may also increase the risk for dementia more in women than in men. In particular, T2D status may interact with serum levels of estrogen to increase risk for dementia. In a recent study, women with type 2 diabetes who were in the highest quartile of serum estrogen concentrations had 14 times the risk for dementia relative to diabetic women with lower estrogen concentrations. Two recent papers from our group support this finding. Women with type 2 diabetes randomized to receive conjugated equine estrogen therapy in the Women's Health Initiative Memory Study (WHIMS) had an increased risk for dementia and lower brain volumes.

### 4.3 JUSTIFICATION FOR DOSE

Women will receive 0.075 mg/day of transdermal estrogen delivered via a Climara patch. Serum estrogen levels will be measured on day 3 of the second week of estrogen administration to titrate levels as needed to attain a circulating level of 50-100pg/ml for each woman. This dosage of estrogen was chosen because it is within physiological limits. Transdermal administration was selected over oral administration because this method of dosing better approximates physiological conditions than oral administration.

#### 4.4 END OF STUDY DEFINITION

A participant is considered to have completed the study if he or she has completed all phases of the study including the last visit or the last scheduled procedure shown in the Schedule of Activities (SoA), Section 1.3.

### 5 STUDY POPULATION

#### 5.1 INCLUSION CRITERIA

In order to be eligible to participate in this study, an individual must meet all of the following criteria:

1. Willing to provide written informed consent
2. Stated willingness to comply with all study procedures and availability for the duration of the study
3. Female, postmenopausal, aged 60-80
4. Normal results on recommended healthcare screenings (e.g., mammogram, pap smear, colonoscopy)
5. BMI 20-35 kg/m^2
6. No evidence of dementia or mild cognitive impairment (MoCA score >25)
7. Women with diabetes, physician diagnosis of type 2 diabetes, or, per American Diabetes Association criteria, showing two markers of dysregulated blood glucose levels at one time (e.g., fasting plasma glucose ≥ 126 mg/dL, 2-hr glucose ≥ 200mg/dL, or elevated HbA1c ≥6.5%) or showing elevated blood glucose using any of these measures at more than one time point.
8. Women with prediabetes, no diagnosis of Type II diabetes and A1c in the pre-diabetic range of 5.7-6.4 or higher.

#### 5.2 EXCLUSION CRITERIA

An individual who meets any of the following criteria will be excluded from participation in this study:

1. Use of hormone replacement therapy within the past 3 months
2. History of renal, heart, liver, or neurological disease; head injury with loss of consciousness in the past 5 years; chronic pain, anxiety or depression
3. Presence of medical conditions that might contraindicate estrogen use (e.g., unexplained vaginal bleeding, history of reproductive tissue cancer, thrombosis)
4. Currently taking insulin, metformin, or any other drug or medication judged by the study physician to affect safety or research outcomes of interest
5. Involved in another research study
6. Contraindications for MRI or PET scanning
7. Current smoker
8. Women without diabetes, no physician diagnosis of type 2 diabetes or prediabetes, and evidence of healthy glucose regulation, indicated by an HbA1c <5.7% and fasting plasma glucose <100mg/dL or 2-hr glucose <140mg/dL.
9. Reporting a level of radiation exposure in the past year that would cause radiation levels to exceed recommended limits if the person participates in this study
10. Participants will be excluded for taking metformin or insulin, other hormone replacement therapies, dantrolene (Dantrium, Ryanodex, Revonto), Viekira Pak (ombitasvir-paritaprevir-

Ritonavir-dasabuvir), carfilzomib (Kyprolis), tranexamic acid (Cyklokapron, Lysteda), hemin (Panhematin), lenalidomide (Revlimid), pomalidomide (Pomalyst), or thalidomide (Thalomid).

As this study targets the effects of estrogen on brain post-menopause, men are excluded.

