## 1 PROTOCOL SUMMARY

### 1.1 SYNOPSIS

Title:	The interaction between diabetes and estradiol on human brain metabolism in postmenopausal women
Study Description:	Epidemiological studies suggest there may be an interaction between type 2 diabetes and estrogen in postmenopausal women, such that diabetes may interact with estrogen levels over time to increase risk for dementia. The mechanism for this effect is now known. However, animal research suggests that it may occur through estrogen's effects on cellular metabolism of glucose and ketone bodies. The primary aim of this study is to test whether type 2 diabetes interacts with estradiol on brain metabolism in vivo in humans. This will be accomplished by imaging brain metabolism using positron emission tomography before and after short-term administration of transdermal 17 $\beta$ -estradiol in 10 postmenopausal women with diabetes and 10 non-diabetic postmenopausal women.
Objectives:	
Primary Objective: The primary objective is to determine whether the effects of glucose and ketone body uptake to the brain in response to 8-week administration of transdermal 17<math>\beta</math>-estradiol differ in postmenopausal women with and without type 2 diabetes.
 
Secondary Objectives: Secondary objective: 1) Determine whether 8-week administration of transdermal 17<math>\beta</math>-estradiol alters cognitive performance in postmenopausal women with and without type 2 diabetes.

Endpoints:	
Primary Endpoint: Glucose and ketone body uptake in brain measures with positron emission tomography. Regions of interest include the posterior cingulate, temporal cortex, and prefrontal cortex.
 
Secondary Endpoints: Cognitive function assessed using composite scores of short-term memory and executive functioning. The short-term memory composite will be generated by summing z-scores from Story Recall, List Learning, and computerized tasks. The executive function composite will be generated by summing z-scores of Trails part B-A, computerized tasks, and semantic access (letter and category word fluency).

Study Population:	Postmenopausal women aged 60-80 years old will be recruited, 10 with type 2 diabetes and 10 without from the region of Forsyth County, North Carolina.
Phase:	N/A

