5.0	12/09/19	5.2 Modify wording of Exclusion Criteria #8 to clarify necessary ranges for cutoff measurements for prediabetic women.	Prediabetic women were all excluded in the past and now are included if measurements fall into this specific range.
6.0	01/28/2020	1.3 Expand length of time between SV1 and SV2 to 1-30 days.	Increasing the span of time allows for more flexibility for scheduling based on participant, equipment and staff availability.
6.0	01/28/2020	8.1 Expand length of time between SV1 and SV2 to 1-30 days	Increasing the span of time allows for more flexibility for scheduling based on participant, equipment and staff availability.
7.0	08/14/2020	10.1.9 Remove reference to DSMB.	There is no Data Safety Monitoring Board for this study.

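### The glycaemic eligibility items in 5.1 and 5.2 contradict the two-group design, and no section says which group eligible prediabetic women join

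*Combined protocol and SAP*

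**What the plan says.** Section 5.2 opens with "An individual who meets any of the following criteria will be excluded from participation in this study". Its item 8 reads "Women without diabetes, no physician diagnosis of type 2 diabetes or prediabetes, and evidence of healthy glucose regulation, indicated by an HbA1c <5.7", and the full set of cutoffs is "HbA1c <5.7% and fasting plasma glucose <100mg/dL or 2-hr glucose <140mg/dL".

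Section 5.1 requires every listed criterion to be met. Item 7 takes women with a physician diagnosis of T2D, women "showing two markers of dysregulated blood glucose levels at one time", or women with a raised value on more than one occasion. HbA1c of 6.5% or more is one of the markers. Item 8 is "Women with prediabetes, no diagnosis of Type II diabetes and A1c in the pre-diabetic range of 5.7-6.4 or higher". No item in 5.1 describes a normoglycaemic woman.

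The synopsis plans "10 postmenopausal women with diabetes and 10 non-diabetic postmenopausal women". Section 4.1 says "It is a single-site study with two comparison groups: one with T2D (n=10) and one without (n=10"), and 5.4 repeats those targets. Footnote 1 of the Schedule of Activities reserves the oral glucose tolerance test (OGTT) for women with neither a diabetes nor a prediabetes diagnosis. Section 2.1 rests the hypothesis on a contrast between healthy and diseased cells.

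Section 9.3 analyses everyone who completes the estrogen administration. Section 9.1 fits an ANCOVA comparing intervention groups, although every woman receives estradiol. The amendment history for version 5.0, used here only as evidence of intent, gives the purpose of the change to exclusion item 8 as "Modify wording of Exclusion Criteria #8 to clarify necessary ranges for cutoff measurements for prediabetic women".

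**The concern.** Diabetes status is the only between-group exposure in this study. If exclusion item 8 is applied as printed, the group without T2D can hold no normoglycaemic women. If it is ignored, each normoglycaemic woman is enrolled against a written criterion.

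The placement of prediabetic women decides what the contrast estimates: T2D against normoglycaemic, T2D against a mixed non-diabetic group, or dysglycaemic against normoglycaemic. The study is unblinded and has 20 women, so a few labels matter. Recruiting to 10 and 10 implies a working label for each woman, but nothing requires that label to be written down or held fixed.

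**Working it through.** **1. The plan's own figure.** The only stated figure is 10 + 10 = 20. Section 9.2 gives no effect size, SD or power, so there is no power calculation to reproduce.

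**2. Logic check.** The three glycaemic items were applied to illustrative profiles (HbA1c %; fasting and 2-hour glucose in mg/dL). Reading A of exclusion item 8 is HbA1c and (fasting or 2-hour). Reading B is (HbA1c and fasting) or 2-hour.

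| Profile | Incl. 7 | Incl. 8 | Excl. 8, A | Excl. 8, B |
|---|---|---|---|---|
| No diagnosis; 5.3, 90, 120 | no | no | **yes** | **yes** |
| Prediabetes diagnosis; 6.0, 110, 150 | no | yes | no | no |
| No diagnosis; 5.8, 95, 130 | no | yes | no | **yes** |
| No diagnosis; 6.6, 115, 160 | no | yes | no | no |
| No diagnosis; 6.6, 130, 160 | yes | yes | no | no |
| T2D diagnosis; 7.0, 140, 220 | yes | no | no | no |

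- Row 1, the normoglycaemic woman, is excluded on either reading and matches no glycaemic inclusion item.
- Row 6, a woman with diagnosed T2D, fails inclusion item 8. If every criterion must be met, she is ineligible too.
- Only row 5 meets inclusion items 7 and 8 together, because item 8 has no upper HbA1c limit and so overlaps the 6.5% marker in item 7.
- Row 3 is both included and excluded under reading B.

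**3. Group for prediabetic women.** Prediabetes appears in the Schedule of Activities footnote, 5.1, 5.2 and the amendment history. None of these assigns a group, and section 9 has no prediabetes category.

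**4. Illustration of size.** The protocol gives no expected number of prediabetic women, so k = 1, 3 or 5 of the 20 is assumed. Other assumptions are no true difference, a two-sided test (9.4.1 gives p<0.05 without sidedness) and a baseline/follow-up correlation of 0.5 or 0.8. The model is follow-up = intercept + group + baseline, with 20 − 3 = 17 residual degrees of freedom and 200,000 simulated trials per cell. Because 9.3 keeps all completers, two classifications are possible: the k women keep their starting group or move to the other. The reported p is the smaller of the two.

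| k | Group sizes after the move | Either rule fixed beforehand | Smaller p chosen afterwards |
|---|---|---|---|
| 1 | 11 v 9 | about 5% | about 7% |
| 3 | 13 v 7 | about 5% | 8.2–8.4% |
| 5 | 15 v 5 | about 5% | 8.9–9.1% |

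**The case against.** Neither list can have been operated literally. Exclusion item 8 opens in parallel with inclusion items 7 and 8, so staff would recognise three group definitions, one of them in the wrong list. That is persuasive on how the error arose. It does not make the text correct: eligibility is checked item by item, and the amendment history ties item 8 to prediabetic women, so the intent is not settled.

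On prediabetic women, the objection is that inclusion item 8 requires no T2D diagnosis and the design groups are with and without T2D, so they fall in the second. This stands as the default reading, but it is an inference. Exclusion item 8 describes women without diabetes as also free of prediabetes, and the open upper limit in inclusion item 8 reaches into the diabetic range.

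Four stronger readings might be inferred, and the documents do not support them:

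- *No comparator could be recruited.* Prediabetic women still fit the label without T2D. The synopsis, 4.1 and 5.4 never use the word healthy. That normoglycaemic women are intended is inferred from 2.1, the OGTT footnote and the wording of item 8. The footnote alone is weak, because a 2-hour glucose could equally serve to apply item 8 as an exclusion.
- *Section 9.1 leaves the exposure undefined.* Both aims name T2D; the reference to intervention groups is loose wording.
- *The false-positive rate could be higher by also dropping prediabetic women.* Section 9.3 includes all completers, so that is not an option under the plan.
- *Classification would be undocumented altogether.* HbA1c, OGTT results, history and chart review are collected at screening under 8.1. What is missing is the group label, not the data behind it.

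**Conclusion.** The eligibility text is wrong as written. Exclusion item 8 and the all-criteria rule in 5.1 both contradict the two-group design, and this follows from the text with no numerical assumption. Misplacement is the likeliest explanation, but a deliberate exclusion of normoglycaemic women cannot be ruled out.

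The missing group rule for prediabetic women is a real but smaller gap, since a plain default exists. The error rates above illustrate it only: they depend on assumed counts and on choosing the classification after the results are known, and a rule fixed beforehand returns the rate to 5%. They are not evidence that anyone has been or will be reclassified. The two readings of item 8's cutoffs are an editorial matter to settle in the same amendment.

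**What to change.** Reconcile 5.1 and 5.2 with the synopsis, 4.1 and 5.4:

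- Move exclusion item 8 to 5.1 as the definition of the comparator. If excluding normoglycaemic women is intended, correct the design text instead.
- Word 5.1 as criteria 1–6 plus one of several mutually exclusive glycaemic definitions. Close the open upper limit in inclusion item 8 against item 7, and make the combination of HbA1c, fasting and 2-hour cutoffs unambiguous.
- State in 4.1 and 9.1, before PET data are analysed, which group prediabetic women join in the primary contrast.
- In 9.1, replace the reference to intervention groups with diabetes-status group.
- Record each woman's group at enrolment.

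An analysis with and without prediabetic women is optional and imprecise. At an assumed effect of 1.325 SD, which gives 80% power for 10 v 10 by a two-sample t test, leaving out five women (10 v 5) gives 61%.

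The cost is a wording amendment and one recorded field. No scans are added, and assigning prediabetic women to a named group needs no extra recruitment.

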## 8 STUDY ASSESSMENTS AND PROCEDURES

### 8.1 ASSESSMENTS

The first visit will be a **screening visit (SV)** to determine if participants meet criteria for enrollment. Screening will be completed 0-3 months prior to beginning the experiment and will take approximately 3 hours. The following will take place during screening:

- An IRB-approved written informed consent will be completed prior to any data collection
- Collection of anthropometric information (height, weight, blood pressure)
- Fasting blood draw (complete blood count (CBC), HbA1c, metabolic panel, lipid panel)
- For non-diabetic women, an Oral Glucose Tolerance Test (OGTT) to assess for diabetes status

- Eat a healthy snack
- Demographic and contact information
- Montreal Cognitive Assessment
- Centers for Epidemiological Studies Depression Scale (CESD-10)
- Detailed self-report health history and review of medications, specifically including smoking status, history of hormone replacement therapy, medical conditions that are contraindicated for estrogen use (listed below under chart review), and radiation exposure in the past year.
- Review of medical record to confirm no evidence of potential contraindications to participate. Specifically, chart review will confirm that relevant screenings such as pap smear and mammogram have been completed in compliance with USPTF recommendations and were negative; assess for a history of the following: unexplained vaginal bleeding, breast cancer, ovarian cancer, blood clots, stroke, myocardial infarction, liver disease, kidney disease, hypothyroidism, endometriosis or fibroids, porphyria, lupus, migraines, or tobacco use. Chart review will also be used to confirm the participant is not taking contraindicated medications.

Between 1-30 days after the screening visit, the results of the screening will be reviewed with the study physician to determine eligibility. If the study physician is traveling for an extended period, she may delegate screening review to another physician during that time. The participant will be notified 0-10 days after eligibility is determined and remaining visits will be scheduled as needed.

The second visit will be **study visit 1 (V1)**. V1 will take place 0-3 months after screening. The following will take place during V1, which will last approximately 2 hours:

- Fasting blood draw for future research, serum estrogen, cortisol, glucose, and insulin levels
- Snack

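### The comparator definition lets a woman with normal HbA1c and fasting glucose but a diabetic-range 2-hour glucose qualify as healthy, which could dilute the group contrast

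*Combined protocol and SAP*

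**What the plan says.** Section 5.2, criterion 8, opens with "Women without diabetes, no physician diagnosis of type 2 diabetes or prediabetes, and evidence of healthy glucose regulation" and then gives the limits: "indicated by an HbA1c <5.7% and fasting plasma glucose <100mg/dL or 2-hr glucose <140mg/dL". There are no brackets. The item stands in a list introduced by "An individual who meets any of the following criteria will be excluded from participation in this study".

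Section 5.1 describes the other two kinds of women. Without a physician's diagnosis, criterion 7 admits a woman as diabetic on "showing two markers of dysregulated blood glucose levels at one time", with the markers given as "fasting plasma glucose ≥ 126 mg/dL, 2-hr glucose ≥ 200mg/dL, or elevated HbA1c ≥6.5"%. Its other route is "showing elevated blood glucose using any of these measures at more than one time point". Criterion 8 describes prediabetes by HbA1c alone: "no diagnosis of Type II diabetes and A1c in the pre-diabetic range of 5.7-6.4 or higher".

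Section 8.1 lists at screening "For non-diabetic women, an Oral Glucose Tolerance Test (OGTT) to assess for diabetes status". The footnote to the schedule in Section 1.3 restricts that test to women with no diagnosis of diabetes or prediabetes. Sections 4.1 and 5.4 plan 10 women with type 2 diabetes and 10 without. Section 9.1 compares the groups by ANCOVA on the follow-up value adjusted for baseline, and uses the same approach for the PET outcomes.

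**The concern.** The hypothesis is that estradiol acts differently in metabolically healthy and metabolically compromised cells, so the contrast depends on the comparator women being metabolically healthy. The oral glucose tolerance test is in the schedule to establish that status. Because *or* joins the fasting and 2-hour limits, an abnormal 2-hour result has no effect on classification once HbA1c and fasting glucose are both below their limits. A woman whose only abnormality is the one this test is designed to find would be filed as healthy. With 10 women per group, each such comparator is a tenth of her arm. If she responds to estradiol as women with diabetes do, she moves the two group means together.

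**Working it through.** **Reading the item.** Applied literally as an exclusion, criterion 8 of Section 5.2 removes every woman with healthy glucose regulation. That contradicts the 10 women without diabetes in Sections 4.1 and 5.4. The item is therefore read here as the definition of the comparator group.

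**Inputs.** From Section 5.2: A = HbA1c below 5.7%, F = fasting glucose below 100 mg/dL, G = 2-hour glucose below 140 mg/dL. From Section 5.1, criterion 7: diabetes markers are fasting glucose at least 126, 2-hour glucose at least 200, HbA1c at least 6.5%. From Section 5.1, criterion 8: prediabetes is HbA1c 5.7% or above.

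**Logic.** The unbracketed sentence can mean A and (F or G), or (A and F) or G. Profiles are HbA1c (%), fasting and 2-hour glucose (mg/dL).

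| Profile | A and (F or G) | (A and F) or G | A and F and G | Diabetes markers | Prediabetes by HbA1c |
|---|---|---|---|---|---|
| 5.6, 95, 250 | meets | meets | fails | 1 | no |
| 5.5, 95, 160 | meets | meets | fails | 0 | no |
| 5.6, 130, 135 | meets | meets | fails | 1 | no |
| 5.5, 110, 210 | fails | fails | fails | 1 | no |
| 6.4, 95, 135 | fails | meets | fails | 0 | yes |
| 5.5, 95, 130 | meets | meets | meets | 0 | no |

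The first row is the defect. She is healthy under both bracketings. One marker at one time does not satisfy the two-marker route of criterion 7. The repeat route would need a second raised value. Her fasting glucose and HbA1c are normal, so that value would have to be another 2-hour result, and the schedule has only one tolerance test.

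**Size, if it occurs.** The plan gives no power, effect size or SD for 10 per group, so there is no figure of its own to reproduce. Let D be the true difference in response between diabetic and healthy women, and let m of 10 comparators respond like diabetic women. The comparator mean moves by (m/10)D towards the diabetic mean, so the expected difference is D(1 − m/10):

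- m = 1: 0.9D, a loss of 10%
- m = 2: 0.8D, a loss of 20%
- m = 3: 0.7D, a loss of 30%

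**Illustrative power.** Assume a two-sided 5% t test, 10 against 10, SD unchanged, and a true standardized difference d. Power comes from the noncentral t distribution with 18 degrees of freedom and noncentrality d(1 − m/10)/√(1/10 + 1/10).

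| Assumed d | m = 0 | m = 1 | m = 2 | m = 3 |
|---|---|---|---|---|
| 1.325 | 80% | 71% | 61% | 50% |
| 1.0 | 56% | 48% | 40% | 32% |

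**How likely is even one?** If a share p of otherwise eligible comparators has the pattern, the chance of at least one among 10 is 1 − (1 − p)^10. For p = 1%, 2%, 5% and 10% this is 10%, 18%, 40% and 65%. All values of p are assumptions.

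**The case against.** **Placement.** As printed, a woman who meets the item is excluded, so she is not counted as a comparator at all. That is correct as a literal reading, and it is a defect in its own right. It does not dispose of this point: the same reading excludes every healthy comparator, and moving the sentence unchanged to the inclusion list would bring the loophole into force. It does mean that changing one word in place repairs nothing.

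**Breadth.** A reader might infer that any woman with a diabetic-range 2-hour value counts as healthy. The documents do not support that. Both HbA1c and fasting glucose must be below their limits; the profile 5.5, 110, 210 fails under both bracketings.

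**Other profiles.** A reader might add the woman with HbA1c 6.4% and 2-hour glucose 135. She passes under one bracketing only and also falls in the prediabetes range of Section 5.1, so she shows an overlap of categories. The woman with fasting glucose 130 and 2-hour glucose 135 does pass both ways. However, fasting glucose is measured again at study visit 1, and a second raised value could bring her under criterion 7. The documents do not say whether that draw is used for classification.

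**Stated contrast.** The plan compares women with and without type 2 diabetes, admits prediabetic women and does not promise a strictly normoglycaemic arm. A comparator with a 2-hour value of 140 to 199 therefore does not breach the stated contrast. This narrows the point to values at or above 200, which conflict with the plan's own diabetes marker.

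**Safeguards.** The study physician reviews screening results, and Section 9.1 allows tolerance-test glucose and insulin as covariates where needed. Review may catch a case, but the written limits give no ground for rejecting her. Women with diagnosed diabetes have no tolerance test, so 2-hour glucose cannot adjust the full comparison, and a covariate does not change group membership.

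**Conclusion.** The concern holds in a limited form. Read as the comparator definition, the item admits as healthy an undiagnosed woman with HbA1c below 5.7%, fasting glucose below 100 mg/dL and a 2-hour value of 200 mg/dL or more. This is so under either bracketing, and no other written criterion reclassifies her on the scheduled screening tests. That conclusion is a matter of logic and needs no assumption beyond reading the item as a group definition.

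The consequence is conditional. A reader might infer that the contrast is diluted. The documents show only that it could be: such women must be enrolled and must respond as diabetic women do, and neither their frequency nor any effect size or SD is given. Under those conditions the loss is m/10 of the expected difference. The power figures depend further on the assumed d and on a t test standing in for the ANCOVA. The repair is cheap and should be made, but the point does not show that the comparison fails.

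**What to change.** 1. Move the item out of the exclusion list and state it as the inclusion (group) definition for the comparator.
2. Require all three limits: no diagnosis of type 2 diabetes or prediabetes, HbA1c below 5.7% AND fasting glucose below 100 mg/dL AND 2-hour glucose below 140 mg/dL. The values should already be in hand: Section 8.1 lists HbA1c and a metabolic panel on the fasting screening draw, and the tolerance test is done in these same women.
3. State that an undiagnosed woman who fails any one limit and meets neither criterion 7 nor criterion 8 of Section 5.1 is a screen failure. Without this, the woman with 5.6, 95, 250 would belong to no group. The profile 5.5, 110, 210 is already in that position under the present text.
4. Reconcile Sections 1.3, 5.1, 5.2 and 8.1. Say which group prediabetic women join. Present criteria 7 and 8 of Section 5.1 as alternatives, since that list requires every item to be met. Settle whether a woman with diagnosed prediabetes has the tolerance test: Section 8.1 offers it to non-diabetic women, while the Section 1.3 footnote leaves her out.

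The cost is a short amendment and a few more screen failures in the comparator group, within the planned screening of up to 200. No new procedure is needed.
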